The dose of metreleptin will be increased beyond 5 mg twice daily (or 0.15 mg/kg/day in patient under 50 kg) only if there is a clear decline in metabolic status without alternative explanations for the metabolic change (such as an infection, noncompliance or dietary indiscretion). It is important to note this because of the wide range of variation in the clinical presentation of these patients, it is impossible to define pre-determined thresholds of metabolic parameters that would appropriately guide dose modifications. Instead, the PI will use best clinical judgment to make dose modifications based on the constellation of metabolic and clinical data available for each patient. Dose escalations will be capped such that the total dose administered will not exceed 0.24 mg/kg/day for any patient without seeking prior permission from the FDA, the NIDDK/ NIAMS IRB and Aegerion Pharmaceuticals, the manufacturer of Metreleptin. If subjects do not tolerate a higher dose level, they can continue the study at the next lowest tolerated dose. Based on previous clinical experience with Metreleptin, tolerance to Metreleptin at doses between 0.12-0.24 mg/kg/day is not expected to be an issue.

Dose reduction:

The dose of metreleptin will be decreased if a subject experiences excessive weight loss (BMI below the normal range for age and sex, or a lesser degree of weight loss that is distressing to the patient). Doses will also be decreased if a subject experiences injection site reactions that cannot be controlled with antihistamines and/or analgesics.

Leptin Withdrawal

For leptin treated subjects, the last dose of leptin will be given on the final day of Period 1 (Day -1) at either 8 am or 8 pm, depending on whether the subject receives once or twice daily dosing. No leptin will be given during Period 2 (Days 0-13). Leptin will be resumed on the morning of Day 14 at the previous dose. In patients who were treated with leptin under protocol 02-DK-0022, we typically recommend tapering of leptin over a 1 week period in patients who stop leptin treatment in an outpatient setting. In contrast, in this protocol, leptin will be stopped without a taper under inpatient observation. The risks of stopping leptin are discussed under Risks.

Pre-study Medications

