Therefore, long-term follow-up data on leptin's effects will not help to answer questions about the energy intake independent effects of leptin. Nonetheless, these data will provide valuable additional information about the time course of leptin's actions in lipodystrophy. Testing during the follow-up visits will mimic that performed during Period 1.

Metabolic Testing

1. Exercise testing: Testing will be performed at the end of Period 1, in the middle and end of Period 2, and during the long-term follow-up visit for subjects in the leptin-naïve group. Skeletal muscle work efficiency will be measured as the increment in energy expenditure above resting energy expenditure during exercise, with lower incremental increase in energy expenditure corresponding to greater muscle work efficiency. This test will be conducted on a cycle ergometer. Following a 10 minute warm-up period, subjects will pedal at 60 rpm with the resistance adjusted to generate 10W of power for 4 minutes. The resistance will then be increased such that the power generated is 25W for 4 minutes, then 50W for 4 minutes. Breath-by-breath oxygen consumption and carbon dioxide production will be collected and averaged every 30 seconds using a metabolic cart (ParvoMedics TrueOne2400, Sandy UT). Heart rate will be monitored by electrocardiograph.
2. Free-living physical activity (actigraphy) will be quantified minute-by-minute using small, portable pager-type and watch accelerometers at the subjects' hip and wrist. Overall physical activity levels, daily changes, amount of time spent in sedentary, moderate, vigorous intensity categories and activity-associated energy expenditures will be extracted [35]. Actigraphy will be conducted continuously throughout the study, beginning on Day -5, and ending on Day 14, and during the long-term follow-up visit for subjects in the leptin-naïve group

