4. Ultrasound of thyroid: This will be performed at Baseline on all enrolled patients with insulin resistance to screen for possible papillary thyroid carcinoma (PTC) since this patient population may be at a higher risk of developing PTC. The testing may also uncover information for future analysis.
5. Other imaging studies as clinically indicated:
 - a. Long bone X-rays to evaluate osseous lesions and to provide further definition as to the natural history of such lesions.

Follow-up

Post-Study Treatment

Subjects newly starting leptin who decide not to complete the entire 19 days of the study will be given the option to continue leptin ad to come back for follow-up and evaluation in six months.

Patients who have generalized lipodystrophy and who reside within the US may continue leptin treatment as an FDA-approved drug through their home endocrinologist. These patients may also continue to receive care at NIH via protocol 76-DK-0006 (Studies of Molecular Genetics of Insulin Secretion, Insulin Action, and Diabetes Mellitus). However, leptin drug supply will not be offered through this study.

Patients who have partial lipodystrophy are not eligible to receive leptin treatment as an FDA-approved drug. In addition, patients with generalized lipodystrophy who do not live in the US cannot obtain FDA-approved drug despite being on-label indication. After completing 6 months of leptin treatment in this study, these patients will have the following options:

1. Taper leptin over 1 week and discontinue the drug
2. Receive leptin through other clinical trials (at NIH or elsewhere) if such trials are available
3. Receive leptin through a compassionate use IND

These choices will be discussed with patients and study staff will assist with decision-making, based on drug availability and the patient's clinical improvement (or lack thereof) with leptin therapy. Regardless of the option chosen, partial lipodystrophy patients and non-US generalized lipodystrophy patients may also continue to receive care at NIH via protocol 76-DK-0006.

Post-Study Obligations

There are no anticipated post-study obligations.

Human Subject Protection

Data and Safety Monitoring Plan

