Non-serious AEs should be followed to resolution or stabilization, or reported as SAEs if they become serious (see Section “Serious Adverse Events Reporting & Collection”). Follow-up is also required for non-serious AEs that cause interruption or discontinuation of study drug and for those present at the end of study treatment as appropriate.

Laboratory Test Result Abnormalities

The following laboratory test result abnormalities should be captured on the non-serious AE CRF page or SAE Report Form as appropriate:

1. Any laboratory test result that is clinically significant or meets the definition of an SAE
2. Any laboratory test result abnormality that required the subject to have study drug discontinued or interrupted
3. Any laboratory test result abnormality that required the subject to receive specific corrective therapy.

It is expected that wherever possible, the clinical rather than laboratory term would be used by the reporting investigator (eg, anemia versus low hemoglobin value).

All identified non-serious AEs must be recorded and described on the non-serious AE page of the case report forms (CRF). Completion of supplemental CRFs may be requested for AEs and/or laboratory abnormalities that are reported/identified during the course of the study.

Serious Adverse events

A Serious adverse event is defined as one of the following (*in accordance with FDA 21 CFR312.32 and the NIH intramural guidance for principal investigators on reporting adverse events*)

- death from any cause,
- life threatening event, i.e., an event that places the subject, in the view of the investigator, at immediate risk of death from the event as it occurred.
- any event that requires or prolongs in-patient hospitalization
- any event that results in persistent or significant disability/incapacity
- any congenital anomaly/birth defect diagnosed in a child of a subject who participated in this study.
- other medically important events that in the opinion of the investigator may jeopardize the subject or may require intervention to prevent one of the other outcomes listed in the definition above.
(Examples of such events include, but are not limited to, intensive treatment in an emergency room or at home for allergic bronchospasm; blood dyscrasias or convulsions that do not result in hospitalization.)

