
Should a patient become pregnant while on study, per 45 CFR 46.204, (1) no inducements, monetary or otherwise, will be offered to terminate a pregnancy, (2) individuals engaged in research will not be involved in any decisions as to timing, method, or procedures used to terminate a pregnancy, and (3) individuals engaged in the research will have no part in determining viability of a neonate.

The investigator must immediately notify the Aegerion Pharmaceuticals (or designee) Medical Monitor of this event and complete and forward a Pregnancy Surveillance Form to United Biosource Corporation (UBC) (or designee) within 7 business days via email to [contact] and [contact].

Follow-up information regarding the course of the pregnancy, including perinatal and neonatal outcome and, where applicable, offspring information must be reported on the Pregnancy Surveillance Form. Any pregnancy that occurs in a female partner of a male study participant should be reported to the sponsor. Information on this pregnancy will be collected on the Pregnancy Surveillance Form.

Overdose

An overdose is defined as the accidental or intentional administration of any dose of a product that is considered both excessive and medically important. All occurrences of overdose must be reported as an SAE.

Serious Adverse Event Collection and Reporting

Following the subject's written consent to participate in the study, all SAEs, whether related or not related to study drug, must be collected, including those thought to be associated with protocol-specified procedures. All SAEs must be collected that occur within 30 days of discontinuation of dosing. The investigator should report

any SAE that occurs after these time periods and that is believed to be related to study drug or protocol-specified procedure.

An SAE report should be completed for any event where doubt exists regarding its seriousness. If the investigator believes that an SAE is not related to study drug, but is potentially related to the conditions of the study (such as withdrawal of previous therapy or a complication of a study procedure), the relationship should be specified in the narrative section of the SAE Report Form.

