- d. **Current lipase > 491 units/L (the upper limit of normal in the NIH assay).** While both amylase and lipase are often used clinically in the assessment of pancreatitis, amylase is a non-specific test that may be elevated for other reasons. Subjects with elevated lipase at study entry will be considered to have laboratory findings consistent with pancreatitis, and will be excluded.

ii. The key element that will minimize risk to subjects is that leptin withdrawal will be performed under close inpatient observation with a controlled diet that should help maintain lower blood glucose and triglycerides. Clinical and laboratory monitoring of subjects for pancreatitis will be performed throughout the period of leptin withdrawal, as follows

- a. Safety labs will be monitored approximately every other day (when research labs are obtained. These will include amylase, lipase, and stool pancreatic elastase. Elevated lipase (greater than the upper limit of normal, 491 units/L) will be a withdrawal criterion. Elevated amylase will be used only as a supportive criterion. Stool pancreatic elastase will be measured primarily for research purposes, as a marker of pancreatic exocrine function. Although triglycerides will be measured along with these labs, isolated elevation of triglycerides, without signs or symptoms of pancreatitis or elevated lipase, will not be a withdrawal criterion.
- b. If pancreatitis is clinically suspected (either based on signs/symptoms consisting of moderate to severe abdominal pain with nausea or vomiting, or based on lipase), the following will take place:
 - i. Amylase and lipase levels will be drawn
 - ii. GI consultation will be obtained
- c. If a diagnosis of pancreatitis is likely or confirmed based on labs and/or GI consultation, the following additional actions will be taken
 - i. Appropriate treatment will be initiated based on GI recommendations (usually, NPO and pain medications)
 - ii. Leptin will be restarted immediately
 - iii. The patient will be withdrawn from the study
 - iv. The IRB will be notified per guidelines for SAEs

4. **Blood Sampling:** Peripheral blood draws (venipuncture) performed during this study for research will not exceed 10.5 mL/kg, or 550 mL (whichever is smaller) per 8-week period for adults. For pediatric

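### No contact is scheduled after leptin restarts in the withdrawal arm, so a late withdrawal-related event such as pancreatitis would be found only by spontaneous report

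*Combined protocol and SAP*

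**What the plan says.** The Leptin Withdrawal section stops leptin on Day -1 without a taper and gives none on Days 0 to 13. It then states: "Leptin will be resumed on the morning of Day 14 at the previous dose". Under Safety Labs, amylase and lipase in this arm are drawn with the fasting research bloods. In the Study Procedures table both of those rows end on Day 13. On Day 14 the table marks only vital signs and bedside glucose. The Metabolic Testing text adds activity monitoring: "Actigraphy will be conducted continuously throughout the study, beginning on Day -5, and ending on Day 14".

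For the main hazard, Risks/Discomforts says: "Clinical and laboratory monitoring of subjects for pancreatitis will be performed throughout the period of leptin withdrawal". It adds that "isolated elevation of triglycerides, without signs or symptoms of pancreatitis or elevated lipase, will not be a withdrawal criterion". The Long-term follow-up section and the second Appendix A calendar cover leptin-naïve subjects only. Post-Study Treatment allows, but does not schedule, continued care under another NIH protocol, and Post-Study Obligations reads: "There are no anticipated post-study obligations".

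On reporting, Serious Adverse Event Collection and Reporting starts at consent and says: "All SAEs must be collected that occur within 30 days of discontinuation of dosing". Beyond that, the investigator should still report "any SAE that occurs after these time periods and that is believed to be related to study drug or protocol-specified procedure". The same section asks for a note in the report narrative when an event may stem from study conditions, and gives withdrawal of earlier therapy as an example. For other events: "Non-serious AEs should be followed to resolution or stabilization, or reported as SAEs if they become serious".

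**The concern.** Reporting rules govern what happens once an event is known. They do not bring it to the study's attention. In this arm the planned observation stops at about the time the intervention is reversed, and no one is assigned to ask the subject afterwards how things went.

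This matters more here than in most small physiological studies. Rationale for Subject Selection says withdrawal subjects can expect no direct benefit, and it rates the pancreatitis risk of withdrawal too high for children to be enrolled in this arm. It also says that experience gained in adults may later support a request to include them. A safety record used that way should rest on active enquiry over a short period after restart.

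A subject can also leave with raised triglycerides, because an isolated rise does not trigger withdrawal. The entry criteria cap triglycerides at 800 mg/dL at study entry but admit pre-leptin values up to 2000 mg/dL.

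**Working it through.** The plan gives no figure to reproduce. The check compares the schedule with the reporting rules.

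1. **Last laboratory check.** Read against the 20 day columns (Day -5 to Day 14), the safety-lab row is marked on Days -5, -1, 0, 2, 4, 6, 8, 10, 12 and 13. Day 14 is blank. The last scheduled lipase therefore falls 14 − 13 = 1 day before restart. The plan allows slight variation in test timing.

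2. **End of inpatient observation.** Study Implementation gives a 19-day stay. Days -5 to 13 are 13 − (−5) + 1 = 19 days. Discharge at about Day 14 is inferred, not stated: the compensation table pays 20 inpatient days and the sample calendar shows admission on Day -6.

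3. **Scheduled contact after Day 14.** The pancreatitis monitoring list covers the withdrawal period. The later visit and its calendar are for leptin-naïve subjects. Post-Study Treatment offers optional care elsewhere. None of these sets a laboratory test, visit or call for the withdrawal arm. Appendix D describes enrolled patients as seen every one to two years, but it does so to justify a consent waiver and sets no safety visit. A routine visit on that cycle would be unlikely to fall within weeks of restart.

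4. **Collection window for serious events.** The rule counts 30 days from discontinuation of dosing and has no provision for subjects who stop and restart.
   - Counted from the Day -1 dose: −1 + 30 = Day 29, which is 29 − 14 = 15 days after restart.
   - Counted from restart, where the off-leptin period ends: 14 + 30 = Day 44.
   - Counted from permanent cessation: no fixed date, since treatment continues.

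   For a subject who leaves early and restarts on, say, Day 5, the first reading still ends on Day 29 (24 days after restart), and counting from restart gives 5 + 30 = Day 35.

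5. **Putting 3 and 4 together.** Every reading covers at least the first 15 days after restart for a completer. The wording is unclear, but it does not exclude the period just after restart. The gap with practical effect is that nothing is scheduled to find an event inside the window.

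**The case against.** The strongest reply is that little risk is left to find. Higher-risk subjects are excluded by triglyceride, lipase and pancreatitis-history criteria. Lipase is checked on Days 12 and 13, and a value above the upper limit ends participation. Restarting leptin is itself part of the plan's response to pancreatitis. Risks/Discomforts reports that at least 25 other patients stopped leptin, half of them without a taper, with no serious event resulting from acute withdrawal, and it judges the short-term risk to be low but not nil. All of this stands, and it keeps the point minor.

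A second reply is that parts of the Risks/Discomforts section and most Day 14 cells of the sample calendar could not be read in the text available for review, so a contact might be described there. That is possible. However, the sections where it would be expected (the pancreatitis monitoring list, long-term follow-up and post-study treatment) are readable and mention none.

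Third, a reader might infer that serious events after Day 14 go unreported, or that the Day 29 reading creates a hole. The documents do not support either. Collection runs from consent, related events remain reportable with no end date, and withdrawal of earlier therapy is named as a cause to note. Serious pancreatitis attributed to protocol-directed withdrawal is arguably reportable under any reading of the window. The Day 29 reading is itself uncertain: the non-serious event section distinguishes interrupting the drug from discontinuing it, and a planned pause fits the former, although Risks/Discomforts does speak of discontinuing leptin in this arm.

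**Conclusion.** The point holds as a minor gap in ascertainment. On the available text the withdrawal arm has no scheduled laboratory test, visit or call after Day 14, so finding a late event depends on the subject or a local physician coming forward. The unclear anchor of the 30-day rule is a secondary matter of wording.

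It would be tempting to go further and say that subjects leave at material risk of pancreatitis. The documents do not support that. They give no triglyceride levels at Day 14 and no estimate of late risk, and what they report on earlier discontinuations points to a low one. No endpoint, power calculation or analysis is affected.

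The conclusion assumes discharge at about Day 14 and that no post-restart contact is described in the parts that could not be read. If one is, only the wording of the 30-day rule needs attention.

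**What to change.** For the withdrawal arm only:

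- Add to the schedule an open-ended telephone contact by existing staff about 7 days after the actual restart: 14 + 7 = about Day 21 for completers, and correspondingly earlier for subjects who leave early and restart at once. Optionally add a second contact about 30 days after restart (about Day 44 for completers). Open-ended questions fit the plan's own instruction not to prompt for specific events.
- Add one sentence to Serious Adverse Event Collection and Reporting: *for subjects whose leptin is withdrawn under this protocol, all serious events are collected from consent until at least 30 days after the actual restart; any longer collection already required continues, and the duty to report later related events is unchanged.* The words *at least* matter. If discontinuation means permanent cessation, a fixed Day 44 end would shorten the present collection.

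No extra laboratory test and no change to dose, restart or discharge is needed. With 10 to 20 subjects, one call each is 10 to 20 calls, and two calls each is 20 to 40. The cost is a little staff time and more minor symptoms recorded. The calls will not detect a lipase rise without symptoms.
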